9.4.3 ANALYSIS OF THE SECONDARY ENDPOINT(S)

Every audio clip (n trials will vary by person, depending on the number of naming attempts) will be coded as 0 for completely or partially unintelligible and 1 for completely intelligible, reflecting speech intelligibility. We will run a logistic mixed effects model with intelligibility as the dependent variable, condition (1-item vs. 9-item) as the independent variable, and random effects of participant and trial. For perceived burden, we will collect responses on three questions/survey for three weeks. Given the small amount of data, survey responses will be plotted to visualize trends in increasing/decreasing burden rather than compared statistically. We will statistically compared averaged burden ratings between participants in the 1-item vs. 9-item condition using t-tests or Wilcoxon rank sum tests (depending on the distribution of the data).

9.4.4 SAFETY ANALYSES

N/A

9.4.5 BASELINE DESCRIPTIVE STATISTICS

Descriptive statistics will include demographics (age, sex, race, ethnicity, and handedness) as well as baseline behavioral testing results, including overall aphasia severity (per the Quick Aphasia Battery), non-linguistic cognitive skills (per the NIH-Toolbox tasks), confrontation naming ability (per the Boston Naming Test and the Snodgrass & Vanderwart probe), and comfort with technology survey data.

9.4.6 PLANNED INTERIM ANALYSES

N/A

9.4.7 SUB-GROUP ANALYSES

No sub-group analyses based on demographics will be performed based on the small sample size for this feasibility study. Instead we will conduct exploratory analyses (see 9.4.9) regarding relationships between personal factors and EMA feasibility metrics.

9.4.8 TABULATION OF INDIVIDUAL PARTICIPANT DATA

Individual participant data will be listed by measure.

9.4.9 EXPLORATORY ANALYSES

We will conduct a series of partial correlations between patient-specific factors and feasibility measures (compliance, completion, speech intelligibility, and perceived burden), controlling for study condition. Patient-specific factors will include age, aphasia severity (derived from the QAB), non-linguistic cognitive skills (averaged performance on the two NIH Toolbox tasks), and a summary score derived from the

Version 1.000

Protocol 15 March 2022

comfort with technology survey. Here, compliance will be the proportion of YES button responses divided by total scheduled trials (YESbutton/756) for each participant. Completion will be the proportion of naming attempts divided by total delivered trials (n naming attempts/n trials delivered). Speech intelligibility will be the proportion of completely intelligible responses divided by the total number of naming attempts (n completely intelligible trials/n naming attempts). Perceived burden will be calculated as the sum of all burden question Likert responses. Multiple comparison correction will be done at a false discovery rate of p < 0.05.

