1.3 SCHEDULE OF ACTIVITIES

Study Phase	Activities
-------------	------------

Pre-EMA Testing

Testing: (1) Quick Aphasia Battery (QAB) to measure overall aphasia severity, (2) the Pattern Comparison Processing Speed Test and Flanker Inhibitory Control and Attention Test from the NIH Cognition Toolbox to measure non-linguistic visual attention and executive functions, respectively, (3) brief, standardized picture description and story elicitation tasks to index anomia in discourse, and (4) an overt object naming test to index word retrieval via a standard SLP assessment format (i.e., single administration in a quiet 1:1 interaction). The naming test will include normed real photos17 of the 260 items from the Snodgrass and Vanderwart stimuli set. PWA will also participate in an intake interview and complete a questionnaire about their comfort with technology, adapted for aphasia (simple language, short phrases).

Smart device training including: (1) Smartwatch Orientation: PWA will be oriented to the smartwatch (interface, charging, etc.) through simple verbal and written instructions and visual demonstrations. (2) EMA Task Training: PWA will be instructed on the specific EMA naming task, including instructions on how to tap on the screen and the optimal approach for providing verbal responses (i.e., mouth close to the watch). Then, PWA will complete an 18-item traditional EMA-style naming task probe (i.e., several trials back-to-back on the smartwatch) in a quiet room in The Aphasia Network (TAN) Lab at Northeastern University. During this probe, SLP graduate student research assistants (RAs) will provide cueing and feedback so that PWA successfully learn how to operate the smartwatch and respond to prompts. (3) EMA Protocol Simulation: PWA will complete a "real-world" EMA task probe in a distracting environment (i.e., coffee shop or university bookstore on Northeastern's campus). For this final activity, over a 45-minute period, 18 smartwatch prompts will be given, either randomly interspersed with one naming trial per prompt (for PWA in the 1-item condition) or split into two sets of 9 trials per prompt (for PWA in the 9item EMA condition). This final activity will mirror the threeweek EMA protocol.

EMA Protocol

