3 OBJECTIVES AND ENDPOINTS

OBJECTIVES	ENDPOINTS	JUSTIFICATION FOR ENDPOINTS	PUTATIVE MECHANISMS OF ACTION
Primary			
Assess EMA compliance in PWA	Compliance will be calculated by dividing the number of answered prompts by the number of scheduled prompts	This metric is often used in describing feasibility of EMA protocols.	N/A - not an intervention
Assess EMA completion in PWA	Completion will be calculated by dividing the number of answered prompts by the number of	Compliance reflects protocol adherence excluding trials missed due to the watch being off/uncharged or a problem with the trial	
	delivered prompts	flow.	
Secondary			
Assess speech intelligibility of EMAs	Recorded responses will be tagged as fully intelligible (1) or partially or completely unintelligible (0)	Speech EMA requires intelligible responses to be clinically useful	N/A - not an intervention
Assess perceived burden from EMAs in PWA	Perceived burden will be calculated by averaging Likert ratings from the Qualtrics survey questions regarding perceived burden	Gathering information about participants experiences with a novel protocol is important for establishing its clinical utility	N/A - not an intervention
Tertiary/Exploratory			
Determine relationships between EMA feasibility metrics and personal factors	N/A	No explicit endpoint are applicable for this objective	N/A - not an intervention

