6.1.2 ADMINISTRATION AND/OR DOSING

In each condition, the smartwatch will vibrate to alert PWA to a single naming trial (1-item condition) or naming trial set (9-item EMA condition). After the vibration alert, PWA will see a screen that says "Ready to name a picture?" (1-item condition) or "Ready to name some pictures?" (9-item EMA condition). If the participant taps YES, a picture will appear, and the device will begin recording audio. PWA will have up to five seconds to provide an oral response, after which a "Thanks!" screen will appear. The fivesecond response window was selected based on research showing that PWA correctly name pictures within 3.5 seconds, on average, with longer response latencies for incorrect responses. If a participant fails to respond to a vibration prompt or pushes the NO button to the "Ready?" screen, they will be reprompted five minutes later via one more vibration alert. During the three-week EMA protocol, each participant will attempt to name 108 unique objects derived from the 260-item Snodgrass and Vanderwart photoset. The subset of pictures presented to each participant will be based on their naming evaluation (during week 1, session 1). When possible, half of the pictures will be items the PWA named correctly during the evaluation, and the other half will be incorrectly named pictures. This approach will allow us to gauge naming variability over time of items PWA are able versus unable to name during traditional SLP assessment, providing an important window into anomia. To mitigate practice effects, the individual pictures (1-item condition) or picture sets (9-item EMA condition) will be presented randomly without replacement until all 108 pictures have been presented, and then the picture cycle will restart. In both conditions, 36 naming trials will be scheduled per day, resulting in a total of 756 scheduled trials for each participant across the experiment. In the 1-item EMA condition, single-naming trial prompts will appear at random intervals from 10am to 8pm. In the 9-item EMA condition, PWA will receive four prompts per day to complete a set of nine picture naming trials per prompt; one prompt will be scheduled in every 2.5-hour block between 10am and 8pm.

15 March 2022

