8.1 ENDPOINT AND OTHER NON-SAFETY ASSESSMENTS

Endpoint Assessments: Feasibility will be classified in three ways: (1) PWAs' adherence to the smartwatch μΕΜΑ or EMA protocol via compliance and completion, (2) PWAs' perceived burden of completing the EMA protocol, and (3) speech intelligibility of recorded naming attempts. Currently, PWAs' capacity for adhering to a smartwatch EMA protocol via button press responses or verbal responses is unknown. As such, compliance will be based on the number of YES button responses to the "Ready?" screen whereas completion will be based on naming attempts. Specifically, similar to [name] et al. (2016), compliance will be determined by the number of YES responses over scheduled trials, including trials missed due to the watch being off/uncharged. Completion will be calculated as trials with captured audio (reflecting attempted naming) over delivered trials, excluding trials missed to the watch being off/uncharged. Perceived burden will be measured via responses to the weekly surveys during weeks 2-4. Finally, speech intelligibility will be measured by a categorical rating of responses captured in each audio clip (i.e., completely intelligible, partially intelligible, or completely unintelligible).

Other Non-Safety Assessments: Before the EMA period, PWA will be administered the following testing battery. The Quick Aphasia Battery (QAB) will be used as our eligibility assessment and to measure overall aphasia severity. The Pattern Comparison Processing Speed Test and Flanker Inhibitory Control and Attention Test from the NIH Cognition Toolbox will be used to measure non-linguistic visual attention and executive functions, respectively. We will use brief, standardized picture description and story elicitation tasks from the AphasiaBank protocol to index anomia in discourse. Participants will complete an overt object naming test twice before EMA and once after EMA so that the research team can evaluate word retrieval via the standard SLP assessment format (i.e., single administration in a quiet 1:1 interaction). This picture naming probe will include normed real photos of the 260 items from the Snodgrass and Vanderwart stimuli set. Before EMA, PWA will also participate in an intake interview and complete a questionnaire about their comfort with technology, adapted for aphasia (simple language, short phrases).

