9.4.2 ANALYSIS OF THE PRIMARY ENDPOINT(S)

We will code each trial in the EMA time series to index compliance, completion, and speech intelligibility. Every scheduled trial (n = 756 total trials) will be coded as 0 for a nonresponse/ NO button

Version 1.000

Protocol 15 March 2022

response or 1 for a YES button response, reflecting compliance. Every delivered trial with a naming attempt captured on audio (n trials will vary by person) will be coded as 0 for incomplete or 1 for complete, reflecting completion. For each of these measures, we will run a logistic mixed effects model with one of the feasibility measures (i.e., compliance, completion) as the dependent variable, condition (1-item vs. 9-item) as the independent variable, and random effects of participant and trial.

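### Compliance lacks a rule linking one set-level YES to nine trials: YESbutton/756 in 9.4.9 caps the 9-item arm at 0.111, and the 80% power in 9.2 does not apply to compliance

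*Combined protocol and SAP*

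**What the plan says.** Compliance is a primary endpoint and is described in four places.

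- Section 3 works per prompt: "dividing the number of answered prompts by the number of scheduled prompts".
- Section 8.1 puts YES taps over trials: "compliance will be determined by the number of YES responses over scheduled trials".
- Section 9.4.2 works per trial: "Every scheduled trial (n = 756 total trials) will be coded", with 0 for a nonresponse or NO, and "response or 1 for a YES button response, reflecting compliance".
- Section 9.4.9 gives a participant-level formula: "compliance will be the proportion of YES button responses divided by total scheduled trials (YESbutton/756) for each participant".

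Section 6.1.2 schedules 36 trials a day in both arms, 756 in all. In the 9-item arm, "PWA will receive four prompts per day to complete a set of nine picture naming trials per prompt". The alert and the ready screen are described once per set. After a NO or no response, "they will be reprompted five minutes later via one more vibration alert".

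Section 1.3 uses the word prompt in two senses. In the training simulation, "18 smartwatch prompts will be given, either randomly interspersed with one naming trial per prompt", and the same sentence then describes the 9-item version as sets of nine trials per prompt.

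Section 9.2 states 80% power for an odds ratio of 1.20, with 10 participants per arm, 756 repeated measures, an AR(1) structure, a correlation of 0.600 and alpha 0.05. The planned model in 9.4.2 has random effects of participant and trial.

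**The concern.** In the 1-item arm a prompt is a trial, so the four descriptions agree. In the 9-item arm they differ by a factor of nine unless a set-level YES is credited to all nine trials of its set, and no section says so. An analyst who takes the 9.4.9 formula as printed and counts taps would put the two arms on different scales within one correlation analysis. Those correlations are meant to show which personal factors go with feasibility.

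The same unit question reaches the sample size. Section 9.2 counts 756 observations per participant in both arms, but compliance in the 9-item arm consists of 84 decisions. The power statement also has to be read against a model that includes a participant random effect.

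**Working it through.** **Counts (6.1.1, 6.1.2).** Three weeks = 21 days.
- Trials, both arms: 36 × 21 = 756.
- Prompts, 1-item arm: 36 × 21 = 756.
- Prompts, 9-item arm: 4 × 21 = 84, and 84 × 9 = 756 trials.
- Re-prompts could raise the alerts in the 9-item arm to 84 × 2 = 168. They follow only a NO or no response, so they add no second YES to a prompt.
- Trials 2 to 9 of accepted sets have no tap of their own: up to 84 × 8 = 672 of 756.

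**The 9.4.9 formula applied to taps.** The maximum in the 9-item arm is 84/756 = 0.111, against 756/756 = 1.00 in the 1-item arm. A 9-item participant who accepts 67 of 84 sets scores 67/756 = 0.089.

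**The carried reading.** If each YES is credited to its nine trials, k accepted sets give 9k/756 = k/84. The same participant scores 603/756 = 67/84 = 0.798, as under Section 3.

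**Effect on the partial correlations.** Assume equal arms, and equal within-arm variances and correlations on the true scale. Controlling for condition removes the difference in arm means. Dividing one arm's scores by 9 leaves
- pooled covariance × (1 + 1/9)/2 = 0.556;
- pooled compliance variance × (1 + 1/81)/2 = 0.506;
- ratio of the partial correlation to its true value = 0.556/√0.506 = 0.78;
- 9-item share of pooled compliance variance = (1/81)/(1 + 1/81) = 1.2%.

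**Reproducing the 9.2 power.** The AR(1) design effect is 1 + 2Σ(1 − k/T)ρ^k. With T = 756 and ρ = 0.6 it is 3.990, so the effective n per participant is 756/3.990 = 189.5. An odds ratio of 1.20 from 0.500 gives 1.2/2.2 = 0.5455. The variance of the log odds ratio is the sum over arms of [SD² + 1/(n p(1 − p))]/10, where SD is the between-participant logit SD. With SD = 0 and 189.5 in both arms, the standard error is 0.0651, ln 1.2 = 0.1823, z = 2.80, and two-sided power is 80%. The stated figure is reproduced.

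**84 decisions in the 9-item arm.** Set starts lie nine trials apart, so their AR(1) correlation is 0.6⁹ = 0.0101 and the effective n is 82.3. With SD = 0 the standard error is 0.0836, z = 2.18, and power is 59%. If consecutive set decisions were more strongly correlated, power would be lower: 48%, 36% and 24% at assumed correlations of 0.2, 0.4 and 0.6.

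**Adding between-participant variance.** The documents give no SD, so these values are assumptions.

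| Logit SD | 756 in both arms | 756 v 84 |
|---|---|---|
| 0 | 80% | 59% |
| 0.25 | 29% | 26% |
| 0.5 | 12% | 12% |
| 1.0 | 7% | 7% |

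Once participants differ, most of the loss comes from that variance. Swapping 84 for 756 would not by itself correct 9.2.

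**The case against.** The strongest reply is that 9.4.2 has a natural reading. Trials 2 to 9 of an accepted set are neither a nonresponse nor a NO, so they take the code 1. Summing those coded trials also gives the right numerator for 9.4.9, and Section 3 then agrees as well. This stands for the primary analysis. It does not remove the gap, because the rule is unwritten and the 9.4.9 formula names button responses as its numerator.

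A reader might infer that the primary arm comparison is biased towards the 9.1 hypothesis of higher compliance in the 1-item arm. The documents do not support that. Section 9.4.9 does not compare arms, and its definition is confined to the exploratory analyses. The arm test is the 9.4.2 model, where the carried coding gives exact proportions. Nor does copying a decision to nine rows disturb that test much. In a simulation of 600 runs per SD with no arm effect, type I error with copied rows against one row per prompt was 6.0% v 5.7%, 6.3% v 6.0% and 4.2% v 4.2% at logit SDs of 0.25, 0.5 and 1.0. That simulation left out the random effect of trial and took decisions as independent given the participant.

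On power, Section 9.2 cites an earlier difference above 0.20 and illustrates its calculation with completed trials. For 0.5 v 0.7 the same approximation, with 756 v 84 observations in the 9-item arm, gives about 100% v 100%, 95% v 94% and 47% v 46% at SDs of 0.25, 0.5 and 1.0. So the unit hardly matters for a difference of that size. The stated 80% for an odds ratio of 1.20 still does not describe the compliance analysis.

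Finally, one YES per set is an inference: 6.1.2 does not describe the screens between pictures within a set. If YES is asked for each picture, the plan should say so.

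**Conclusion.** The point holds as a gap in the definition of a primary endpoint, a printed exploratory formula that fails on tap counts in one arm, and a power statement that does not apply to compliance. It should be fixed before analysis.

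The cap of 0.111 rests on one YES per set. The 0.78 attenuation rests also on equal within-arm variances and correlations, and on an analyst using tap counts. The 59% assumes zero between-participant variance and the document's AR(1) correlation carried over nine steps. The 26%, 12% and 7% rest on assumed SDs and show a range, not an estimate.

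No bias in the primary arm test is claimed. The four sections are not irreconcilable either, since one sentence on crediting a set-level YES brings them into line.

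**What to change.** - **Sections 3 and 8.1:** define compliance once, as prompts accepted with YES at the alert or its re-prompt, over scheduled prompts. The denominator is 756 in the 1-item arm and 84 in the 9-item arm.
- **Section 9.4.9:** use YES/756 or YES/84 according to arm.
- **Section 9.4.2:** either fit one row per prompt, and say what the trial random effect then indexes, or state that a set-level YES is credited to all nine trials. The proportions are identical, and the second option leaves the model as written.
- **Section 9.2:** state that the 80% for an odds ratio of 1.20 assumes 756 AR(1) observations in both arms and no between-participant variance, and so does not apply to compliance. Give power over a range of participant SDs.

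Completion and intelligibility stay at trial level. The cost is wording in five sections and at most minor recoding, with no new data. The downside is that the stated power for compliance becomes less favourable.

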For three weeks, PWA will name aloud pictures that appear on the smartwatch as they go about their daily activities. At the end of each week, PWA will complete a virtual check-in with the study team at which time they will also complete a brief (16-item) Qualtrics survey about their EMA experiences that week.

Version 1.000

Protocol 15 March 2022

Post-EMA Protocol Testing	In a final session, PWA will complete the overt object
and Exit Interview	naming test in standard SLP format once more. Finally,
	they will participate in an exit interview about the study.

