7.1 DISCONTINUATION OF STUDY INTERVENTION/EXPERIMENTAL MANIPULATION

If the study term observes several time periods of missed trials, they will address the issue with a participant during the weekly check-in. As feasibility is the cornerstone of this trial, the study team will not discontinue participants for reasons related to protocol adherence.

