7.3 LOST TO FOLLOW-UP

A participant will be considered lost to follow-up if they fail to return for three scheduled check-ins or sessions and study staff are unable to contact the participant after at least 3 attempts. The following actions will be taken if a participant fails to return to the lab for a required study visit:

- The site will attempt to contact the participant, reschedule the missed visit or check-in, counsel the participant on the importance of maintaining the assigned visit schedule, and ascertain if the participant wishes to and/or should continue in the study
- Before a participant is deemed lost to follow-up, the investigator or designee will make every effort to regain contact with the participant (where possible, 3 telephone calls and/or emails). These contact attempts will be documented in the participant's study file.
- Should the participant continue to be unreachable, they will be considered to have withdrawn from the study with a primary reason of lost to follow-up.

15 March 2022

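### Section 9.4.9 scores perceived burden as a sum while Sections 3 and 9.4.3 average it, so a missed weekly survey can distort the exploratory correlations

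*Combined protocol and SAP*

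**What the plan says.** Section 3 (Objectives and Endpoints) defines the endpoint: "Perceived burden will be calculated by averaging Likert ratings from the Qualtrics survey questions regarding perceived burden". Section 9.4.3 follows that definition for the test between conditions: "We will statistically compared averaged burden ratings between participants in the 1-item vs. 9-item condition". The same section gives the amount of data: "we will collect responses on three questions/survey for three weeks".

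Section 9.4.9 introduces the exploratory work with "We will conduct a series of partial correlations between patient-specific factors and feasibility measures". These correlations control for condition, and the factors are age, aphasia severity, non-linguistic cognition and comfort with technology. Here the score changes: "Perceived burden will be calculated as the sum of all burden question Likert responses". The other three measures in that section (compliance, completion, intelligibility) are proportions with a stated denominator. Burden is the only one without a denominator.

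The documents give no rule for an incomplete set of surveys: no prorating, no imputation and no minimum number.

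**The concern.** A sum and an average carry the same information only if everyone answers the same number of items. Partial survey data are possible under this protocol. The survey is taken at a weekly contact (Section 1.3: "At the end of each week, PWA will complete a virtual check-in with the study team"). Section 7.1 keeps poor adherers in the study ("the study team will not discontinue participants for reasons related to protocol adherence"). Under Section 7.3 a participant is lost to follow-up only on failing, after repeated contact attempts, to "fail to return for three scheduled check-ins or sessions". Someone who misses one or two check-ins therefore stays in the analysis with 6 or 3 responses instead of 9.

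A sum over whatever was answered then depends on how many surveys were answered as well as on how burdensome the protocol felt. Section 5.3 expects some people with severe aphasia to find participation harder. Aphasia severity and comfort with technology, both plausibly related to missing an online survey, are two of the four factors being correlated. An apparent link between severity and burden could then be a link between severity and survey completion.

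**Working it through.** The plan states no figure for the burden score, so there is none to reproduce.

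**Inputs from the documents.** 3 burden questions per survey and 3 weekly surveys (Section 9.4.3); 10 + 10 participants (Section 6.1.1); 4 personal factors and 4 feasibility measures, with false discovery rate control (Section 9.4.9).

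**Step 1: how the two scores relate.** Let k be the number of surveys answered and m the mean rating of the answered items. Then sum = 3 x k x m, and average = m.

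- k = 3: sum = 9m. This is a fixed multiple of the average, so every correlation is identical.
- k = 2: sum = 6m, and 6/9 = 0.67, a fall of 33% at a constant rating.
- k = 1: sum = 3m, and 3/9 = 0.33, a fall of 67%.

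**Step 2: an example.** A participant who always rates 4 has a sum of 36, 24 or 12 with 3, 2 or 1 surveys answered; the average is 4.0 each time. A participant who always rates 3 and answers everything has a sum of 27. With one survey missed, the sum ranks the first participant below the second (24 v 27), while the average ranks them 4.0 v 3.0.

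**Step 3: effect on the partial correlation.** The documents give neither missing rates nor the rating scale, so this step is a simulation on assumptions: 20 participants, a 5-point scale, between-person SD 0.7, item SD 0.8, and severity truly unrelated to burden. Whole surveys are missed at one rate in the more severe half and another in the rest. Participants with no survey are left out, and the partial correlation controls for condition. There were 5,000 simulated studies per scenario. The r shown is the absolute value of the average over studies.

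| Missed surveys, more severe half v the rest | Sum: spurious absolute r | Sum: false positives at 0.05, unadjusted |
|---|---|---|
| None, or equal in both halves | 0 | about 5% |
| 10% v 5% | about 0.07 | about 6% |
| 20% v 5% | about 0.20 | about 13% |
| 30% v 10% | about 0.25 | about 17% |

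With the mean of the answered items, r is about 0 and false positives are about 4% to 5% in the two widest scenarios.

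**Step 4: the planned correction.** If all 4 x 4 = 16 correlations form one family, the strictest step of the false discovery rate procedure is 0.05/16 = 0.0031. At that threshold the sum gives about 1.5% false positives at 20% v 5% and about 2.4% at 30% v 10%. The rates in the table are therefore not those of the planned analysis. The correction does not remove the bias in r itself, and 1.5% and 2.4% are still above the 0.3% that this threshold would allow an unbiased score.

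**Step 5: another reading of the sum.** If an incomplete sum were set to missing, the 30% v 10% scenario would give r of about 0 and about 5.2% false positives. The price is data. With independent misses, the expected number of complete participants is 10 x 0.7^3 + 10 x 0.9^3 = 3.43 + 7.29 = 10.7 of 20.

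**The case against.** The strongest reply is that the harm needs a scoring rule that the plan does not state. Section 9.4.9 does not say how an incomplete set is scored; if incomplete sums are set to missing, the bias disappears (Step 5). This stands. It is why a reader should not infer that the rule gives a wrong result whenever a survey is missed: the bias also needs missingness related to the factor being correlated.

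Second, missed surveys may be rare. The survey is completed at a check-in with staff, Section 5.5 plans weekly contacts with participants or their care providers, and Section 7.3 calls for a missed check-in to be rescheduled. Nothing in the documents supports 30% v 10%, and at 10% v 5% the effect is small. This also stands, so the size has to be given as a range that starts at zero.

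Third, two further inferences are tempting but unsupported. One is that a participant who answers no survey scores 0 and looks least burdened: the plan does not say whether that person scores 0 or is missing, and three missed check-ins with failed contact count as withdrawal under Section 7.3. The other is that non-responders look less burdened: this assumes that higher codes mean more burden, and the coding is not given. With the opposite coding the direction reverses, although the dependence on the number of surveys answered remains.

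What the reply leaves untouched is that one endpoint has two scores, with no reason given for the switch and no missing-survey rule.

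**Conclusion.** The inconsistency is real, and its effect is conditional. With complete data nothing changes. With missed surveys counted into the sum as it stands, the score mixes burden with adherence; if the misses are related to severity or comfort with technology, the exploratory correlations are biased by an amount that the documents cannot fix. On the assumptions in Step 3 the spurious absolute r lies between 0 and about 0.25.

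The reach is narrow. A reader might infer that the secondary burden comparison or the primary endpoints are compromised. They are not: Section 9.4.3 already uses averages, and compliance and completion do not use this score. Nor can the analysis simply be called a secondary objective. The synopsis and Section 4.2 call it secondary, but Section 3 lists it as tertiary/exploratory with no explicit endpoint. It is worth correcting because the correction is nearly free and because Section 9.4.7 relies on these correlations in place of subgroup analyses.

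**What to change.** In Section 9.4.9:

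- Replace the sum with the mean of the answered burden items, the score already used in Sections 3 and 9.4.3.
- Treat participants with no answered survey as missing, not as 0, and state the minimum number of surveys needed for a score.
- State the Likert scale and which end means more burden.
- Report the number of surveys answered per participant, so that a relation with severity or comfort with technology can be seen. A table by condition alone would not show it.

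The mean still assumes that the answered weeks represent the missed ones, and the per-participant counts let a reader judge that. The cost is a few sentences of analysis wording and no new data. If every survey is answered, no correlation changes.
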